4.3. Biosafety: N/A

4.4. Stem Cells: N/A

5. Procedures Involved

[figure not shown]
5.1. Study Design:

The RCT among 368 eligible melanoma survivors will be conducted in two Waves (two consecutive summers), with planned adjustments to improve recruitment, compliance and participant retention between study Waves, see Figure 3. Wave 1 may enroll up to 184 participants, though given logistical constraints due to working from home during the pandemic, fewer may be recruited, with the plan to obtain the full 368 by the end of Wave 2.

Figure 3. Phase 2 Study Design.

PROTOCOL TITLE: Wearable device intervention to improve sun behaviors in melanoma survivors

VERSION DATE: 07/19/2021

5.2. Study Procedures –Randomized Controlled Trial:

Randomization. Following written consent and completion of the baseline survey, participants will be randomized with a 1:1 ratio to the intervention or control arm. Randomization will be stratified by age (<50 years, 50+ years), gender, years since melanoma diagnosis (<2 years, 2-5 years, 6-9 years) and highest melanoma stage (I, II, III/IV). We will use block randomization with random blocks of size 2 and 4 to improve balance. The staff recruiting and enrolling participants will be blinded to their randomization. The study statistician will use R to generate random sequence numbers based on the stratified, block randomization scheme and upload the allocation list to REDCap. Following consent and screening, the study coordinator at the University of Minnesota will randomize participants.

Study Initiation. Following randomization, participants will then be mailed their device in early summer (with appropriate version of the mobile app based on randomization) and study assigned log-in information. This will include a study-created user name to be used with the device/mobile app to allow for direct retrieval of the device-collected data by the study coordinator. Participants will also be provided written training materials. Participants will be provided with a study phone number and email to contact the study coordinator with any remaining technical issues or questions.

PROTOCOL TITLE: Wearable device intervention to improve sun behaviors in melanoma survivors

VERSION DATE: 07/19/2021

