6.3. Release/Sharing

Data collected in this study will not be released or shared to those outside of the research team.

7. Sharing of Results with Participants

7.1. All participants (regardless of randomization group) will be provided a summary report of their personal sun exposure during the intervention period. Study results will not be shared with the participants nor will study participation be shared with their providers. Participants will have access to their own data captured by the device via their mobile application.

8. Study Population

8.1. Inclusion Criteria:

- 18-75 years old

PROTOCOL TITLE: Wearable device intervention to improve sun behaviors in melanoma survivors

VERSION DATE: 07/19/2021

- Diagnosed with cutaneous invasive melanoma within HealthPartners system since 2010
- Able to read/write in English
- Own a smartphone
- Able to provide voluntary informed consent

8.2. Exclusion Criteria:

- Inability to provide informed consent
- Pregnancy
- Patients who have opted out of their records being used for research purposes

8.3. Screening:

To identify eligible participants, HealthPartners medical claims data will be queried to identify members diagnosed with melanoma during the recruitment eligibility period (2010-forward). HealthPartners members who have a melanoma diagnosis (2 or more codes) between 2010 and the beginning of the study recruitment period will be queried from the VDW or ADW Administrative Claims database. If additional subjects need to be identified to meet recruitment goals, then HealthPartners or Park Nicollet patients who are not HealthPartners members will be queried from EMR data in the EPIC/Clarity database. ICD9 and ICD10 Codes of 172.xx and C43.xxx respectively will be used to identify eligible members or patients. Tumor registry data within the VDW may also be utilized to identify members or patients diagnosed with melanoma. Those identified as potentially eligible will be mailed an invitation letter from HealthPartners and contacted by phone to confirm eligibility.

9. Vulnerable Populations

9.1. Vulnerable Populations:

Population / Group	Identify whether any of the following populations will be targeted, included (not necessarily targeted) or excluded from participation in the study.

PROTOCOL TITLE: Wearable device intervention to improve sun behaviors in melanoma survivors

VERSION DATE: 07/19/2021

Children	Excluded from Participation
Pregnant women/fetuses/neonates	Excluded from Participation

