To identify eligible participants, HealthPartners medical claims data will be queried to identify members diagnosed with melanoma during the recruitment eligibility period (2010-forward). HealthPartners members who have a melanoma diagnosis (2 or more codes) between 2010 and the beginning of the study recruitment period will be queried from the VDW or ADW Administrative Claims database. If additional subjects need to be identified to meet recruitment goals, then HealthPartners or Park Nicollet patients who are not HealthPartners members will be queried from EMR data in the EPIC/Clarity database. ICD9 and ICD10 Codes of 172.xx and C43.xxx respectively will be used to identify eligible members or patients. Tumor registry data within the VDW may also be utilized to identify members or patients diagnosed with melanoma. HealthPartners will be the only site of recruitment.

11.3. Recruitment Materials:

Participants will be mailed an introductory letter outlining the study purpose and providing an email address / phone number to contact the study coordinator if interested. HealthPartners will then follow-up by phone to obtain verbal consent to provide their contact information to the University of Minnesota. The University of Minnesota will then mail or email individuals an introductory letter and either paper consent and HIPAA forms (mail) or a link to access online consent and HIPAA forms. All recruitment materials are provided with the protocol.

11.4. Payment:

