Statistical analysis will focus on evaluating the efficacy, unintended consequences and implementation of the intervention in this RCT. The main analysis of the primary outcome (self-reported overall sun protection score) will be a two-sample two-sided two-sample t-test comparing scores at the end of the intervention period (12 weeks) between intervention and control groups. Randomization should result in two groups that are similar for patient characteristics and other extraneous factors that may influence sun exposure and protection behaviors, however, we will compare the randomized groups by Wave, gender, age, stage of disease, device use (low/high), and baseline measures of sun protection and exposure behaviors using two-sample t-tests and Chi-squared tests to identify potential confounding factors which may not be balanced between the two groups. We will supplement the primary analysis with a multivariate linear regression model to account for any identified differences at baseline. A secondary analysis will explore changes in the sun protection score over the intervention period (baseline, weeks 4, 8 and 12) using a mixed effects regression model. This analysis will not be completed until both Waves have been conducted.

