21.2. International Research: N/A

22. Multi-Site Research

N/A

23. Resources Available

PROTOCOL TITLE: Wearable device intervention to improve sun behaviors in

melanoma survivors

VERSION DATE: 07/19/2021

23.1. Resources Available:

Funding: This study will be conducted with grants to [name] from the American Cancer Society and Melanoma Research Alliance.

Research team: All investigators are committed to this project and will provide appropriate effort as needed. [name] will have a study coordinator who will be supported 50% time to conduct the study.

Participant Availability: HealthPartners is the largest consumer-governed nonprofit health care organization in the country, providing care, coverage, research, and education to improve health and well-being in partnership with its members, patients and community. Founded in 1957, the HealthPartners family of care serves more than 1.5 million medical and dental health plan members and more than 1 million patients. The organization includes a multispecialty group practice of more than 1,700 physicians; 7 hospitals; 47 primary care clinics; 22 urgent care locations; 22 dental clinics; and numerous specialty practices in Minnesota and western Wisconsin. Given very low levels of uninsured in Minnesota (single-digit percentages over the past decade), high population penetration of managed care in the state, and a high health insurance market-share, the HealthPartners member and patient populations are generally representative of the larger population.

Using data from HealthPartners 2010-2016, we expect over 2000 members will meet our eligibility criteria. We have previously found melanoma survivors to be highly motivated to participate in research, with participation rates of 70-85% for interviews and focus groups. While this is a more intensive study, we anticipate no issues recruiting 248 individuals.

The research outlined in this protocol was presented to the Cutaneous Oncology Translational Working Group in December 2017 and was met with enthusiasm from the dermatologists, surgeons, and oncologists treating patients with melanoma at the University of Minnesota. They verbally agreed to support this study and should recruitment by HealthPartners become a concern, University of Minnesota/Fairview patients may be considered.

UNIVERSITY OF MINNESOTA

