Appendix: Summary of Protocol Changes and Rationale – 01/27/2020

Major changes:

1. The original version of this protocol was funded by the American Cancer Society. We also received funding for usability and a pilot study version of this proposed work from the Melanoma Research Alliance (protocol STUDY00002107/2018NTLS002). We negotiated to combine the funding to support one larger study to increase our power for experience of sunburn during the intervention period, a key secondary outcome. Therefore, we have increased the sample size here from 248 to 368 (184 each wave/summer) and we will formally close the previous pilot study with the CPRC, IRB and CT.gov and add the Melanoma Research Alliance as a funding source for this protocol. The PI discussed this plan of action with [name] on 1/24/2020 who agreed this would likely be the best path from the IRB perspective.
2. After our usability testing we have decided to switch to a different wearable device than originally proposed. This device, Shade, was developed in collaboration with the NIH NCI and has been shown to be significantly more accurate than our previously proposed device. One disadvantage of this device is that it does not objectively measure physical activity as the previous device did and therefore those pieces were removed from the protocol. We will rely on self-report measures of physical activity to test our secondary hypotheses related to physical activity. Additionally, this device is significantly more expensive than the previously planned device and therefore participants will be asked to return the device at the end of the intervention period and be provided gift cards throughout the study as incentive instead. They will be provided up to \$120 in gift cards if they complete all study procedures (\$20 baseline survey, \$10 week 4 survey, \$10 week 8 survey, \$60 return device and complete week 12 survey, \$20 complete week 64 survey).
3. As this is a minimal risk study, we have removed the during-study monitoring of anxiety and depression. We have found in another study of cancer survivors that this monitoring and sending of letters often confuses and distresses participants. We will plan, however, to examine whether rates of anxiety and/or depression rise during the intervention period (week 12 vs. baseline) following Wave 1. While we do not expect that to be the case, should it happen we will proactively monitor in Wave 2.

Minor changes:

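### Do the randomization strata for years since diagnosis leave participants 10 or more years out with nowhere to go?

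*Combined protocol and SAP*

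**What the plan says.** Section 5.2 (Randomization) allocates 1:1 within strata of age (two levels, the upper one open-ended), gender, "years since melanoma diagnosis (<2 years, 2-5 years, 6-9 years) and highest melanoma stage (I, II, III/IV"), using random blocks of 2 and 4. The study statistician generates the list and loads it into REDCap, and the coordinator then randomizes.

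Section 8.1 admits anyone "Diagnosed with cutaneous invasive melanoma within HealthPartners system since 2010". Section 8.3 describes the search as covering "HealthPartners members who have a melanoma diagnosis (2 or more codes) between 2010 and the beginning of the study recruitment period", and section 11.2 repeats it: "HealthPartners medical claims data will be queried to identify members diagnosed with melanoma during the recruitment eligibility period (2010-forward"). Neither the inclusion nor the exclusion criteria limit time since diagnosis.

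Section 15.3 makes the main analysis a "two-sample t-test comparing scores at the end of the intervention period (12 weeks) between intervention and control groups". It contains no term for the stratification factors.

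**The concern.** A stratified list needs a level for every eligible person. Age has an open top level, but years since diagnosis stops at 9. Someone diagnosed in early 2010 and randomized in spring 2020 or later is past that limit. Read literally, the rule has no cell for such a person, so staff would have to choose one or turn away an eligible, consented survivor. If the choice were made inconsistently or left unrecorded, the report could not say exactly how these participants were allocated. The factor also matters to the subject: Table 1 in section 4.1 lists, as a barrier to sun protection, the diagnosis receding into the past.

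**Working it through.** **1. Does the calendar create the gap?** The change summary dated 01/27/2020 (used only for dating) still looks ahead to Wave 1. Section 5.1 plans Wave 1 under pandemic conditions: "given logistical constraints due to working from home during the pandemic, fewer may be recruited, with the plan to obtain the full 368". Section 11.1 recruits in spring, over two consecutive years. Wave 1 is therefore spring 2020 at the earliest, and Wave 2 is 2021 at the earliest. A January 2010 diagnosis reaches 10 years in January 2020, so both Waves include eligible people beyond the top level. Counting in completed years does not remove them.

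**2. How many people?** The documents give neither the Wave years nor the distribution of diagnosis dates, so this step rests on assumptions. Let W be the recruitment date as a decimal year, and let diagnoses have density proportional to exp(r(t − 2010)) from 2010 to W. The share at 10 or more years is

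(exp(r(W − 2020)) − 1) / (exp(r(W − 2010)) − 1),

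which for r = 0 becomes (W − 2020)/(W − 2010).

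| Assumed r | W = 2020.3 | W = 2021.3 | W = 2022.3 |
|---|---|---|---|
| 0 (even spread) | 0.3/10.3 = 2.9% | 1.3/11.3 = 11.5% | 2.3/12.3 = 18.7% |
| 0.05 | 2.2% | 8.8% | 14.3% |
| 0.10 | 1.7% | 6.6% | 10.7% |

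With equal Waves, the trial-level count is 368 times the mean of two adjacent columns:

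- 2020 and 2021: 27 (r = 0), 20 (r = 0.05), 15 (r = 0.10)
- 2021 and 2022: 56, 43, 32

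A recruitment date of 1 April with an even spread gives 0.25/10.25 = 2.4%, 1.25/11.25 = 11.1% and 2.25/12.25 = 18.4%. That is about 25 or 54 of 368. Section 5.1 allows a smaller Wave 1, which would move these counts toward the Wave 2 share.

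**3. Do the design figures use the strata?** Section 15.2 expects 314 with outcome data; 368 × 0.85 = 312.8, which agrees closely. For 157 per arm, effect size 0.40 and two-sided 0.05, power is Φ(0.40 × √(157/2) − 1.96) = Φ(1.58) = 94.3% (94.2% by the noncentral t), against 95% stated. For sunburn, 20% against 10% gives 70.1%, against 70% stated. None of these inputs involves years since diagnosis.

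**4. Does the analysis use the strata?** The main test compares arm means at week 12 without them. The supplementary regression in 15.3 adjusts for differences found at baseline. Diagnosis date is obtained under section 5.4 and year of diagnosis in Table 2, so any adjustment can use the actual time, whatever the stratum was called.

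**5. Would more levels help?** As written there are 2 × 2 × 3 × 3 = 36 cells (two gender levels assumed), or 368/36 = 10.2 people per cell on average. An open top level keeps 36. A separate level for 10 or more years gives 2 × 2 × 4 × 3 = 48 cells and 368/48 = 7.7 per cell. That thins the cells further for a factor the primary test does not use.

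**The case for a change.** The strongest case for acting is that the contradiction between 5.2 and 8.1 is definite, that no reading of the 6-9 level removes it, and that the correction is a few words. In addition, 15.3 does not name years since diagnosis among the factors to be compared between arms, so stratification is the only named control on it, and it omits the longest-out survivors.

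The textual mismatch stands, and so does the absence of any stated placement. The consequence does not follow. The documents do not show the REDCap stratum fields, so it is not established that anyone had to improvise. The person who builds the list must give every eligible record a level, and the level adjoining 10 years is the obvious one. Used that way, it still balances long-out survivors between the arms as a group. If such people had instead been left out, that would have happened before allocation. It would narrow the enrolled population, but it would not bias the comparison of the arms.

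Two smaller gaps yield to the same ordinary practice. A person at five and a half years has a level once years are counted as completed years. The reference diagnosis is not named, but the diagnosis that made the person eligible is the natural choice.

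Timing also weakens the case. The current version is dated 07/19/2021 and recruitment is in spring. If the summers were 2020 and 2021, enrolment was probably over and a new label would govern nobody.

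**Conclusion.** No change to the plan follows. The closed top level is a clerical slip that whoever builds the allocation list can fill in one sensible way. It may concern roughly 15 to 56 of 368 participants, on the assumed diagnosis distributions, equal Waves and the two calendars considered; a later calendar would raise the number. The conclusion does not depend on that count. It rests on three facts: assignment within any level fixed before allocation is still random at 1:1, the power figures and the primary t-test make no use of the strata, and the actual diagnosis date is held for any adjusted analysis. It does assume that these participants were classified from baseline information before allocation. The documents do not show this directly, but nothing in them suggests otherwise.

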5.5. Use of radiation: N/A

5.6. Use of Center for Magnetic Resonance Research: N/A

6. Data and Specimen Banking

6.1. Storage and Access

All data (collected by the wearable device and survey data) will be stored in REDCap. REDCap includes features to support HIPAA compliance with a full audit trail, user-based privileges, and integration with the institutional LDAP server. Only members of the research team will have access to the data.

Data collected by the wearable devices: The study coordinator will use the study user names to access the device use data via the Shade clinical trials dashboard. The data are maintained de-identified (study user ID only) indefinitely as part of the Shade dashboard and can be exported as a CSV or Excel file. The study coordinator will view the data of all participants (both intervention and control) weekly to monitor device use. Following the completion of the intervention period, the study coordinator will download the final device data which will be combined and merged with the REDCap survey data for statistical analysis.

Survey data: Survey data will be collected and stored in REDCap ³³. The study survey will be accessible from any location with an internet connection. REDCap allows users to exit and return to the survey at any time without losing data. As the participant completes the questionnaire, the data are entered directly into the REDCap database, which uses a MySQL database via a secure web interface with data checks to ensure data quality.

6.2. Data:

Self-administered questionnaire data will be collected at baseline, 4, 8, 12 and 64 weeks post-randomization (see Table 2 above).

Demographics and Disease Information. Demographics will be ascertained at the baseline survey and will include age, race/ethnicity, income, education, employment status, relationship status, skin type and family history of cancer. Disease information will include disease stage, tumor location, treatments received and co-morbidities.

PROTOCOL TITLE: Wearable device intervention to improve sun behaviors in

melanoma survivors

VERSION DATE: 07/19/2021

Outcomes Measures. Outcomes will be measured via self-reported online surveys and the Shade device (see Section 3.0). Study outcomes include reliable and validated measures used previously by the study team and will be scored following standard procedures.

Process Measures. We will focus on a number of metrics regarding study implementation, including recruitment, compliance/engagement, retention, and satisfaction/usability of the device. Recruitment metrics will include a proportion of eligible individuals who agree to participate and number of contacts required to recruit a participant. Measures of compliance and engagement will focus on device set-up and intervention usage, including time from recruitment to device use, average number of days the device is worn per week, number of times the study coordinator contacted to remind use, and self-reported engagement/response to the UVR notifications on the mobile app. Study retention will be measured as the proportion of participants who complete the baseline and each of the follow-up surveys. Finally, we will measure satisfaction with the device. The implementation metrics will be examined after Wave 1 is complete in order to identify areas of opportunity to improve recruitment, compliance/engagement and retention that can be implemented prior to starting Wave 2. While we will keep the intervention consistent across Waves, we will consider alternative methods of recruitment, incentives, reminders, and other actions to maximize engagement and retention.

6.3. Release/Sharing

Data collected in this study will not be released or shared to those outside of the research team.

7. Sharing of Results with Participants

7.1. All participants (regardless of randomization group) will be provided a summary report of their personal sun exposure during the intervention period. Study results will not be shared with the participants nor will study participation be shared with their providers. Participants will have access to their own data captured by the device via their mobile application.

8. Study Population

8.1. Inclusion Criteria:

- 18-75 years old

PROTOCOL TITLE: Wearable device intervention to improve sun behaviors in melanoma survivors

VERSION DATE: 07/19/2021

- Diagnosed with cutaneous invasive melanoma within HealthPartners system since 2010
- Able to read/write in English
- Own a smartphone
- Able to provide voluntary informed consent

8.2. Exclusion Criteria:

- Inability to provide informed consent
- Pregnancy
- Patients who have opted out of their records being used for research purposes

8.3. Screening:

To identify eligible participants, HealthPartners medical claims data will be queried to identify members diagnosed with melanoma during the recruitment eligibility period (2010-forward). HealthPartners members who have a melanoma diagnosis (2 or more codes) between 2010 and the beginning of the study recruitment period will be queried from the VDW or ADW Administrative Claims database. If additional subjects need to be identified to meet recruitment goals, then HealthPartners or Park Nicollet patients who are not HealthPartners members will be queried from EMR data in the EPIC/Clarity database. ICD9 and ICD10 Codes of 172.xx and C43.xxx respectively will be used to identify eligible members or patients. Tumor registry data within the VDW may also be utilized to identify members or patients diagnosed with melanoma. Those identified as potentially eligible will be mailed an invitation letter from HealthPartners and contacted by phone to confirm eligibility.

9. Vulnerable Populations

9.1. Vulnerable Populations:

Population / Group	Identify whether any of the following populations will be targeted, included (not necessarily targeted) or excluded from participation in the study.

PROTOCOL TITLE: Wearable device intervention to improve sun behaviors in melanoma survivors

VERSION DATE: 07/19/2021

Children	Excluded from Participation
Pregnant women/fetuses/neonates	Excluded from Participation
Prisoners	Excluded from Participation
Adults lacking capacity to consent and/or adults with diminished capacity to consent, including, but not limited to, those with acute medical conditions, psychiatric disorders, neurologic disorders, developmental disorders, and behavioral disorders	Excluded from Participation
Non-English speakers	Excluded from Participation
Those unable to read (illiterate)	Excluded from Participation
Employees of the researcher	Excluded from Participation
Students of the researcher	Excluded from Participation
Undervalued or disenfranchised social group	Included/Allowed to Participate
Active members of the military (service members), DoD personnel (including civilian employees)	Included/Allowed to Participate
Individual or group that is approached for participation in research during a stressful situation such as emergency room setting, childbirth (labor), etc.	Excluded from Participation
Individual or group that is disadvantaged in the distribution of social goods and services such as income, housing, or healthcare.	Included/Allowed to Participate
Individual or group with a serious health condition for which there are no satisfactory standard treatments.	Included/Allowed to Participate

PROTOCOL TITLE: Wearable device intervention to improve sun behaviors in melanoma survivors

VERSION DATE: 07/19/2021

Individual or group with a fear of negative consequences for not participating in the research (e.g. institutionalization, deportation, disclosure of stigmatizing behavior).	Excluded from Participation
Any other circumstance/dynamic that could increase vulnerability to coercion or exploitation that might influence consent to research or decision to continue in research.	Excluded from Participation

9.2. Additional Safeguards:

All participants will have had a melanoma diagnosis, which is a serious health condition. This study specifically aims to understand and intervene on sun risk behaviors among melanoma survivors. Therefore, melanoma survivors are the explicit target population of this study.

The proposed research will not specifically seek military members or DOD personnel, disadvantaged individuals or members of undervalued or disenfranchised social groups, however, if volunteers meets the inclusion criteria and also happen to be from one of the groups checked above, they will be eligible to participate in the study.

10. Local Number of Participants

10.1. Local Number of Participants to be Consented as Eligible for Recruitment (Verbal): 460

Local Number of Participants to be Consented to Full Study (Written): 390

11. Local Recruitment Methods

11.1. Recruitment Process:

Trained and experienced staff of HealthPartners Institute Center for Evaluation and Survey Research (CESR) will oversee the recruitment process. The CESR has been engaged in research both within the HealthPartners patient/member population and broader community for more than 15 years and is directed by a seasoned PhD survey methodologist and health services researcher, who oversees staff of

PROTOCOL TITLE: Wearable device intervention to improve sun behaviors in melanoma survivors

VERSION DATE: 07/19/2021

bachelors and masters-level employees with experience and training in survey, interview, chart-audit, and electronic data capture for research purposes. The CESR employs REDCap (Research Electronic Data Capture)³³ as a primary data capture and management platform.

To recruit the required sample size and ensure meaningful measures of protection sun exposure, participants will be enrolled in two cohorts (Wave 1 and 2) over two consecutive summers. Recruitment will occur in the spring with the study intervention running over the summer both years to account for seasonality.

Potential participants identified by HealthPartners in the screening process will be randomly assigned to a mailing round (2 rounds of approximately n=500 each within each Wave). Each round will be mailed 2 weeks apart to ensure phone contact is proximal to the mail date. We will send potential subjects a letter on HealthPartners letterhead introducing the general nature of the study and the elements of informed consent, and notifying the participant that a study interviewer will soon call. Subjects will be provided a study phone-number, which they may contact if they would like more information about the study. The letter will state that the information obtained is confidential and that participation is voluntary. Next, within two weeks of sending each letter, an interviewer trained specifically on this study protocol will phone the subject to ask if he or she is willing to participate in the study if they have not opted out. The interviewer will obtain verbal consent to participate in the study and for their contact information (name, address, phone number) to be shared with members of the University of Minnesota research staff. If such consent is provided, it will be documented and their names and contact information will be so forwarded. All subsequent contact with these individuals in conjunction with this study will be conducted by study staff at the University of Minnesota

Once the goal of consenting participants has been reached for a given Wave, a wait-list will be created which will be used to replace individuals who do not complete the formal study consent process and baseline survey. Given our expectation of losing approximately 15% of individuals after this initial agreement, HealthPartners will provide the University of Minnesota with contact information for additional individuals.

The University of Minnesota staff will then contact individuals provided by HealthPartners by mail or email in spring to confirm their interest in participating in the study and obtain written or electronic informed consent and HIPAA forms along with their preferred form of contact for study communication.

PROTOCOL TITLE: Wearable device intervention to improve sun behaviors in

melanoma survivors

VERSION DATE: 07/19/2021

11.2. Identification of Potential Participants:

To identify eligible participants, HealthPartners medical claims data will be queried to identify members diagnosed with melanoma during the recruitment eligibility period (2010-forward). HealthPartners members who have a melanoma diagnosis (2 or more codes) between 2010 and the beginning of the study recruitment period will be queried from the VDW or ADW Administrative Claims database. If additional subjects need to be identified to meet recruitment goals, then HealthPartners or Park Nicollet patients who are not HealthPartners members will be queried from EMR data in the EPIC/Clarity database. ICD9 and ICD10 Codes of 172.xx and C43.xxx respectively will be used to identify eligible members or patients. Tumor registry data within the VDW may also be utilized to identify members or patients diagnosed with melanoma. HealthPartners will be the only site of recruitment.

11.3. Recruitment Materials:

Participants will be mailed an introductory letter outlining the study purpose and providing an email address / phone number to contact the study coordinator if interested. HealthPartners will then follow-up by phone to obtain verbal consent to provide their contact information to the University of Minnesota. The University of Minnesota will then mail or email individuals an introductory letter and either paper consent and HIPAA forms (mail) or a link to access online consent and HIPAA forms. All recruitment materials are provided with the protocol.

11.4. Payment:

Participants will be provided gift cards by mail throughout the study period as they complete study procedures. They will receive \$20 following completion of the baseline survey, \$10 for the week 4 survey, \$10 for the week 8 survey, \$60 for returning the device at the end of the study period and completing the week 12 survey, and \$20 for the week 64 survey (for a total of up to \$120). In addition, a lottery-based incentive will be used to promote adherence. This incentive structure will indirectly support behavior change by incentivizing use of the devices rather than directly incentivizing the direct sun-exposure behavior. Participants will be entered into weekly lotteries for \$100 gift cards for the duration of the intervention period (12 weeks; lotteries will be held up to 16 weeks given the rolling recruitment). The weekly winners will be randomly drawn from all participants. The randomly selected winners will only be eligible for the prize if they wore the device at least 5 days during that week, as evidenced by activity data. We will email the study group every week indicating that

PROTOCOL TITLE: Wearable device intervention to improve sun behaviors in

melanoma survivors

VERSION DATE: 07/19/2021

the lottery was drawn, a winner was chosen, and the number of draws required to obtain a participant who was eligible to win.

12. Withdrawal of Participants

12.1. Withdrawal Circumstances:

No participant will be withdrawn from the study against their will.

Participants will only be withdrawn from the study if they ask to withdraw or become too ill or die prior to completing the study. If participants become too ill, they will not be withdrawn from the study until they have given their voluntary consent for study withdrawal.

12.2. Withdrawal Procedures:

Participants that withdraw from the study for any reason will be noted in the REDCap study database and will no longer receive contact from study personnel. The data collected up until that point will be used in data analysis unless otherwise requested by the participant.

12.3. Termination Procedures:

Participants will not be terminated from this study without their consent as this is a randomized controlled trial and all participants are to be followed regardless of their device use.

13. Risks to Participants

13.1. Foreseeable Risks:

This study carries minimal risk and will comply with the University of Minnesota IRB reporting requirements. We identified the following 2 possible risks to subjects:

Risk to confidentiality: Participants will be asked to keep their mobile phone password protected to guard their confidentiality. Inadvertent breaches of confidentiality by investigators or their staff are unlikely but may occur.

Identifying information will be kept private and all identifiers will be removed prior to any data being given to researchers. The records will be identified only with a unique ID number on an encrypted database. Data transfer will only occur with de-identified data with encrypted transfer of all information containing protected health information between participants and study databases.

PROTOCOL TITLE: Wearable device intervention to improve sun behaviors in

melanoma survivors

VERSION DATE: 07/19/2021

Discomfort with survey questions: There is a possibility that some participants may feel uncomfortable being asked questions about their melanoma diagnosis and health behaviors.

